### **2.5.3 Handling of intercurrent events**

The underlying question for the primary estimand is: what is the effect attributable to different doses of GT005 on GA change on FAF at Week 48 in subjects who have not received alternative GA medications or therapies in the study eye.

For this estimand, data following the below intercurrent event will be dealt with in the following specific way:

- Subject receives alternative GA medications or therapies in the study eye: GA lesion size data collected in the study eye after the subject initiates alternative GA medications or therapies will be censored and imputed assuming missing at random.

### **2.5.4 Handling of missing values not related to intercurrent event**

In the case of missing data occurring in other scenarios, i.e. independent of intercurrent events defined in [Table 1-2](#), the estimand based on an MAR approach will be considered specifically for each treatment arm the subjects are assigned.

### **2.5.5 Sensitivity analyses**

Not applicable.

### **2.5.6 Supplementary analyses**

Not applicable.

## 2.6 Analysis supporting secondary objectives

There are six secondary objectives:

1. Evaluate the effect of GT005 on the progression of GA in subjects with GA due to AMD
2. Evaluate the safety and tolerability of GT005
3. Evaluate the effect of GT005 on retinal anatomical measures
4. Evaluate the effect of GT005 on functional measures, BCVA and LLD
5. Evaluate the effect of GT005 on visual function, MNRead and FRI
6. Evaluate the effect of GT005 on patient-reported outcomes

### 2.6.1 Secondary endpoint(s)

The corresponding secondary endpoints are:

1. Change from baseline through Week 96 in GA area as measured by FAF
2. Frequency of treatment emergent adverse event (AE) through Week 96
3. Change in retinal morphology on multimodal imaging through Week 96
- 4.a Change in best corrected visual acuity (BCVA) Score via the early treatment for diabetic retinopathy (ETDRS) chart through Week 96
- 4.b Change in low luminance difference (LLD) via the ETDRS chart through Week 96
- 5.a Change in reading performance as assessed by Minnesota low-vision reading test (MNRead) chart through Week 96
- 5.b Change in functional reading independence (FRI) index through Week 96
6. Change in quality of life measured on the visual function questionnaire-25 (VFQ-25) through Week 96

### 2.6.2 Statistical hypothesis, model, and method of analysis

1. Change from baseline through Week 96 in GA area as measured by FAF
  - MMRM as described in [Section 2.5.2](#) will be applied to the change from baseline through Week 96 in GA area, with intercurrent events and missing data handled in the same way as for the primary estimand ([Section 2.5.3](#)).

The estimated least-squares mean (LSM) for the change in GA area, and treatment difference against untreated control, as well as the corresponding 90% confidence interval, will be summarized by visit and treatment groups. A line plot for the estimated LSM with 90% CI by visit and treatment groups will also be provided. All assessments of GA area will be listed by treatment group, site, and subject.

2. Frequency of treatment emergent adverse event (AE) through Week 96

- The summary tables for treatment-emergent serious AE (TESAE) will be presented as described in [Section 2.7.1](#).
- Subjects who did not receive treatment due to surgical procedure related AEs will be listed separately by treatment group.

3. Change in retinal morphology on multimodal imaging through Week 96

- The presence of the following retinal morphology will be summarized based on observed data by visit for the number and percentage of subjects in reported categories:
  - i. Junctional zone of GA (Increased FAF, Normal FAF, Not Applicable, Cannot Grade) assessed by FAF.
  - ii. Junctional zone patterns (Atypical, Banded, Diffuse, Focal, Cannot Grade) assessed by FAF.

4.a Change in best corrected visual acuity (BCVA) Score via the early treatment for diabetic retinopathy (ETDRS) chart through Week 96

- The change in BCVA through Week 96 will be estimated among treatment groups via least squares means from a MMRM model. The model will include the change from baseline in BCVA measured by ETDRS as the dependent variable, BCVA at the baseline as the covariate, assessment visit, treatment group, two interaction terms (assessment visit and treatment group, assessment visit and BCVA at the baseline) as the fixed effect and participant as a random effect. The estimated least-squares mean (LSM) for the change in BCVA, and treatment difference against untreated control, as well as the corresponding 90% confidence interval, will be summarized by visit and treatment groups. A line plot for the estimated LSM with 90% CI by visit and treatment groups will also be provided. All BCVA assessments will be listed by treatment group, site, and subject.

4.b Change in low luminance difference (LLD) via the ETDRS chart through Week 96

- The LLD and the changes from baseline will be summarized based on observed data by assessment visits and treatment group. All LLD assessments will be listed by treatment group, site, and subject.

5.a Change in reading performance as assessed by Minnesota low-vision reading test (MNRead) chart through Week 96

- The Maximum reading speed (MRS) for each eye as assessed by MNRead Chart and the change from baseline will be summarized based on observed data by visit and treatment group. Reading speed (words per minute) will be computed for each of the 19 sentences read using the following formula:
$$60 \times \max(0, 10 - \text{number of errors}) / \text{reading time in seconds}$$
The mean of three higher reading speeds will be reported as the maximum reading speed.

### 5.b Change in functional reading independence (FRI) index through Week 96

- The FRI index and the changes from baseline will be calculated and summarized based on observed data by assessment visits and treatment group.

6. Change in quality of life measured on the visual function questionnaire-25 (VFQ-25) through Week 96

- The VFQ-25 sub-scales and composite scores and the changes from baseline will be calculated and summarized based on observed data by assessment visits and treatment group.

As this study is being terminated, statistical modeling and/or summary tables for corresponding endpoints will be provided as appropriate based on data availability.

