### 2.3.2 Demographics and other baseline characteristics

Demographic and baseline characteristics including age, race, (self-reported and genetically defined) ethnicity, sex, and AMD genetic subgroup will be summarized with descriptive statistics or counts and percentages of subjects as appropriate by treatment group and in total for FAS.

Summary statistics will be presented for the study eye if they are baseline ocular characteristics. Listings for demographic and ocular baseline characteristics will be provided.

Baseline ocular characteristics for the study eye will be summarized by treatment group and in total for the FAS. Ocular baseline characteristics include:

- Study eye selection (left eye OS or right eye OD)
- Best corrected visual acuity BCVA (in ETDRS letters)
- Low-luminance visual acuity (LLVA) (in ETDRS letters)
- Low luminance deficit (LLD) (BCVA - LLVA in ETDRS letters)
- GA lesion area (mm^2) as assessed by FAF
- GA contour (Unifocal, Multifocal, Cannot Grade) as assessed by FAF
- GA foveal involvement (Foveal, Non-foveal, Cannot Grade) as assessed by FAF and optical coherence tomography (OCT)
- Junctional zone pattern (Atypical, Banded, Diffuse, Focal, Cannot Grade) as assessed by FAF
- Presence of hard drusen (Yes, No, Cannot Grade) as assessed by color fundus photography (CFP)
- Presence of soft drusen (Yes, No, Cannot Grade) as assessed by CFP
- Presence of calcified drusen (Yes, No, Cannot Grade) as assessed by CFP
- Presence of cuticular drusen (Yes, No, Cannot Grade) as assessed by CFP
- Presence of subretinal hemorrhage (Yes, No, Cannot Grade) as assessed by CFP
- Presence of intraretinal hemorrhage (Yes, No, Cannot Grade) as assessed by CFP
- Presence of reticular pseudodrusen (Yes, No, Cannot Grade) as assessed by OCT
- Central Subfield Thickness (CSFT) (μm) as assessed by OCT
- Years since GA diagnosis

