## 4 Change to protocol specified analyses

The Week 48 interim analysis was removed.

The Safety Analysis Set (SAF) was removed.

The estimand framework was simplified. Analysis for the primary endpoint was changed to MMRM.

Subgroup of interest is not applicable.

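### SAP 2.6.2 item 3 analyses the multimodal retinal-morphology change endpoint with two FAF junctional-zone features counted by visit, giving no change summary and no OCT or CFP feature under this endpoint

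*SAP*

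**What the plan says.** The third secondary objective in SAP 2.6 is to "Evaluate the effect of GT005 on retinal anatomical measures". Its endpoint in SAP 2.6.1, worded the same way in Protocol Section 2, is "Change in retinal morphology on multimodal imaging through Week 96". Neither document lists the features that make up retinal morphology.

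SAP 2.6.2 item 3 gives the analysis. It opens "The presence of the following retinal morphology will be summarized based on observed data by visit", as numbers and percentages in the reported categories, and then lists two features:

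- "Junctional zone of GA (Increased FAF, Normal FAF, Not Applicable, Cannot Grade) assessed by FAF"
- "Junctional zone patterns (Atypical, Banded, Diffuse, Focal, Cannot Grade) assessed by FAF"

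The list is closed, shows no redaction mark, and refers to no other section.

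SAP 2.3.2 has a wider list of ocular characteristics at baseline. It includes features read on OCT or CFP, for example "Presence of subretinal hemorrhage (Yes, No, Cannot Grade) as assessed by CFP".

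SAP Section 4 sets out the departures from the protocol. It covers removal of the Week 48 interim, removal of the safety set, the change stated as "The estimand framework was simplified. Analysis for the primary endpoint was changed to MMRM", and the dropped subgroup. It does not mention retinal morphology.

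**The concern.** The endpoint has two defining words, change and multimodal, and the analysis in item 3 delivers neither.

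On change: counts by visit show the distribution of categories at each visit. They do not show which eyes moved from one category to another, and movements in opposite directions cancel. Because the summary uses observed data, the set of eyes also differs from visit to visit. In a study that ended early, a shift in percentages could reflect who was still being imaged.

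On multimodal: both features come from FAF. If item 3 is followed as written, the study report would answer the retinal-anatomy objective from one modality under a heading that promises several. A reader of the report would have no signal that the scope had been cut, because Section 4 does not say so.

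**Working it through.** No power, sample-size or error-rate figure is involved. The check compares lists.

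**1. Features analysed under the endpoint (SAP 2.6.2 item 3).** There are two: junctional zone of GA and junctional zone patterns. From FAF: 2 of 2. From OCT or CFP: 0 of 2.

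**2. Baseline features that use OCT or CFP (SAP 2.3.2).**

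| Modality | Features | Count |
|---|---|---|
| CFP | hard, soft, calcified and cuticular drusen; subretinal and intraretinal haemorrhage | 6 |
| OCT | reticular pseudodrusen; CSFT | 2 |
| FAF with OCT | GA foveal involvement | 1 |

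The total is 6 + 2 + 1 = 9. Item 3 carries 0 of these 9 forward.

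**3. Are the images scheduled after baseline in both arms?** Protocol Tables 1 and 2 both schedule OCT-Macula at Weeks 12, 24, 36, 48, 72 and 96, which is six common visits. Both schedule CFP at Weeks 48, 72 and 96, which is three. Protocol 7.3.3 and 7.3.5 send all of these images to the central reading centre. This shows that images should exist. It does not show that each feature was graded after baseline.

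**4. Is change analysed elsewhere in SAP 2.6.2?** Seven of the endpoints in SAP 2.6.1 are worded as changes: 1, 3, 4.a, 4.b, 5.a, 5.b and 6. For six of them (all but 3), SAP 2.6.2 specifies change from baseline. Item 3 is the only one without it. Its first feature, junctional zone of GA, is also not named in the baseline list of SAP 2.3.2, although FAF is taken at screening.

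**5. Is there a follow-up summary in the readable safety sections?** SAP 2.7 covers adverse events, events of special interest, deaths, loss of visual acuity, laboratory values and vital signs. It contains no summary of reading-centre OCT or CFP gradings.

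**6. Does anything readable declare the narrowing?** SAP Section 4 does not. The closing sentence of SAP 2.6.2 makes outputs depend on available data because of termination, but it drops no named feature.

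**The case against.** The strongest reply is that this is a matter of labelling.

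- **The protocol lists no morphology features**, and its Section 9.4.2 asks only for counts and percentages for categorical endpoints, which item 3 provides. A baseline list describes the population and creates no duty to tabulate every item later. This stands. It is why the fix below takes up only four of the nine features (foveal involvement, CSFT and the two haemorrhage items). It does not answer the absence of change or of a second modality in an endpoint defined by both.

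- **A reader might infer that the OCT and CFP features are analysed nowhere.** The documents do not support that. The SAP contents page has two entries without readable titles between 2.10 and Section 3, and part of the safety text in Protocol 9.4.3 is blacked out. Some of these features may be analysed there.

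- **A reader might also infer that the between-arm comparison of anatomical harm is lost.** That goes too far. SAP 2.7.1 tabulates adverse events by treatment group for study and fellow eye, with surgery-related events separately. SAP 2.7.1.1 covers events of special interest, and SAP 2.7.3 covers losses of at least 15 and at least 30 letters. A reported haemorrhage or detachment would appear. These are investigator reports made with knowledge of allocation (Protocol 3.4.1), whereas imaging efficacy assessments at the reading centre are fully masked. They do not replace the endpoint, but the channel exists.

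- **Acute bleb-related detachment is not a good argument for more tables.** The protocol says blebs usually flatten within about 24 hours (Synopsis) and that structural recovery generally takes up to 1 month (1.6.1.2). Controls have no post-baseline OCT before Week 12. Tables starting at Week 12 or Week 48 would largely miss such effects. No document says which anatomical features are most likely to differ between arms.

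- **Modelling CSFT by MMRM** would exceed what LLD, MNRead, FRI and VFQ-25 receive in SAP 2.6.2, namely observed-data summaries. This stands, and a descriptive summary is enough.

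**Conclusion.** The mismatch is real and confined to this endpoint. SAP 2.6.2 item 3, as written, yields neither a change nor a multimodal result for the retinal-anatomy objective: 2 of 2 features are FAF, 0 of 9 OCT- or CFP-based baseline features are followed, and there is no baseline-to-visit comparison. The narrowing is not declared in Section 4.

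The primary analysis is untouched. What is at stake is whether a secondary endpoint is reported as what it claims to be. The conclusion rests on the readable text and says nothing about the redacted sections. It also does not assume that the OCT and CFP features were graded after baseline. The figure of approximately 202 subjects is the planned number and should not be used to size the lost information: SAP Section 1 states that the study is being terminated early after a futility interim analysis.

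**What to change.** In SAP 2.6.2 item 3, for the study eye, by treatment group and on observed data, add the following, each where the reading centre graded the feature after baseline:

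1. Baseline-to-visit shift tables for the two junctional-zone items and for foveal involvement. The first junctional-zone item needs a baseline grade, so it should also be added to the list in SAP 2.3.2.
2. A descriptive summary of CSFT change from baseline at Weeks 12, 24, 36, 48, 72 and 96. No MMRM is needed.
3. The number and percentage of eyes with new subretinal or intraretinal haemorrhage on CFP at Weeks 48, 72 and 96, among eyes without it at baseline.

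If OCT and CFP features were not graded after baseline, label the output *FAF junctional-zone morphology* and record the narrowing in SAP Section 4, so that the study report does not present it as multimodal.

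The cost is a few more descriptive tables from images already scheduled and sent to the reading centre, with no new visit or procedure. The downside is that late-visit data will be limited because of early termination. The fallback costs only wording.

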**Table 3: Prohibited Medications for Study Eye Only**

Medication	Prohibition period for GT005 arm	Prohibition period for untreated control arm	Action taken
Investigational GA medication	Week 96	Week 96	Record in eCRF and continue with study visits until end of study
Approved GA medication	Week 96	Week 48	Record in eCRF and continue with study visits until end of study

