### **2.1.1.6 Alternative GA medications or therapies**

Avacincaptad pegol (Izervay) and pegcetacoplan (Syfovre) via intravitreal injection are Food and Drug Administration approved treatments for GA and are permittable alternative GA treatments in this study.

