### **2.6.3 Handling of missing values/censoring/discontinuations**

Missing data handling of secondary analyses for different endpoints are specified in [Section 2.6.2](#).

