### **2.7.1 Adverse events (AEs)**

Only AEs that occurred during the study period (from the date of randomization to the end of study) will be summarized. AEs recorded after screening but before the date of randomization will be listed only.

**Treatment-emergent Adverse Event (TEAE):** An adverse event is considered treatment emergent if the start date/time of the event is on or after the date of randomization, irrespective of the treatment arm. The primary summaries of AEs will be based on TEAEs.

The number (and percentage) of subjects with AEs will be summarized separately for ocular (study eye and fellow eye) and non-ocular events by treatment group in the following ways unless otherwise specified:

- Overall summary of death, subjects with any AE, any severe AE, any study treatment-related AE, any surgical procedure related AE, any AE leading to study discontinuation, any serious AE (SAE), any study treatment-related SAE, any surgical procedure related SAE, any SAE leading to study discontinuation
- AEs by primary SOC and PT
- AEs related to study treatment by SOC and PT (separately for study eye and non-ocular)
- AEs related to surgical procedure by SOC and PT (separately for study eye and non-ocular)
- SAEs by primary SOC and PT

- SAEs related to study treatment by SOC and PT (separately for study eye and non-ocular)
- SAEs related to surgical procedure by SOC and PT (separately for study eye and non-ocular)

A subject with multiple adverse events within a primary SOC is only counted once towards the total of the primary SOC.

All AEs, deaths, and SAEs (including those from the pre- and post-treatment periods) will be listed and those collected after the use of alternative GA therapies/medications, or during the pre-treatment, post-study period will be flagged. In addition, subjects who are not receiving treatment due to surgical procedure-related AEs will be listed separately by treatment group.

The MedDRA version used for reporting the AEs will be described in footnote.

For the legal requirements of ClinicalTrials.gov and EudraCT, two required tables on “on-treatment/treatment emergent” adverse events which are not serious adverse events with an incidence greater than 2% (or other cutting point as appropriate) and on “on-treatment/treatment emergent” serious adverse events and SAE suspected to be related to study treatment will be provided by system organ class and preferred term on the safety set population (i.e., the FAS of this study).

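### After Week 48 only controls may take approved GA drugs in the study eye, and the SAP censors for this in GA area alone, so late study-eye function and safety results may mix untreated and treated control data

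*SAP*

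**What the plan says.** Protocol Table 3 gives the GT005 arm's period first; the next column is headed "Prohibition period for untreated control arm". Its row for approved products reads "Approved GA medication Week 96 Week 48 Record in eCRF and continue with study visits until end of study". The bar therefore lasts to Week 96 for GT005 and to Week 48 for controls, and a subject who starts such a drug remains in the study.

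SAP 2.1.1.6 names two FDA-approved intravitreal drugs and says that they "are permittable alternative GA treatments in this study". It states no limit by arm or by time.

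SAP Table 1-2 and 2.5.3 define one intercurrent event, study-eye use of an alternative GA therapy: "GA lesion size data collected in the study eye after the subject initiates alternative GA medications or therapies will be censored and imputed" under a missing-at-random assumption. SAP 2.6.2 item 1 extends this to GA area through Week 96.

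For BCVA, 2.6.2 item 4.a says "The change in BCVA through Week 96 will be estimated among treatment groups via least squares means from a MMRM model" and lists the model terms, without a rule for this event. SAP 2.6.3, whose title includes censoring, says "Missing data handling of secondary analyses for different endpoints are specified in" Section 2.6.2.

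For adverse events, 2.7.1 says of the listings that "those collected after the use of alternative GA therapies/medications, or during the pre-treatment, post-study period will be flagged".

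**The concern.** From Week 48 the comparator can change, under protocol-compliant use, in one arm only. The SAP deals with this for GA area and is silent for the other study-eye results. At Weeks 72 and 96 the GA-area rows then address GT005 against no alternative therapy. The BCVA rows address GT005 against no treatment followed, for some controls, by an approved drug. Both appear as a difference from untreated control with a 90% confidence interval, and nothing tells the reader that the questions differ.

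For safety the likely direction matters. A study-eye event following an intravitreal injection in a control would be tabulated under untreated control. That raises the control rate and makes GT005 look relatively better tolerated. For BCVA, any effect of the drug would move the control mean.

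**Working it through.** **1. Rules side by side.** Handling of data collected after alternative GA therapy in the study eye:

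| Result | SAP section | Rule |
|---|---|---|
| GA area to Week 96 | 2.5.3; 2.6.2 item 1 | Censored, missing at random |
| Retinal morphology | 2.6.2 item 3 | Observed data; none |
| BCVA | 2.6.2 item 4.a | MMRM; none |
| LLD, MNRead | 2.6.2 items 4.b, 5.a | Observed data; none |
| FRI, VFQ-25 (person-level) | 2.6.2 items 5.b, 6 | Observed data; none |
| ≥15/≥30-letter loss to Week 96 | 2.7.3 | None |
| TEAE tables, randomisation to end of study | 2.7.1 | Flag in listings; no split in tables |

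Sensitivity and supplementary analyses of the primary objective are marked not applicable (2.5.5, 2.5.6), and none is listed for the secondary endpoints. The gap is in the text and needs no arithmetic.

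**2. How much late follow-up could exist.** Part 2 opened only after V6.0 approvals (Protocol 1.5.2 and the Figure 1 footnote). V6.0 is dated 6 December 2022 and the SAP 24 January 2024.
- Interval: 365 + 49 = 414 days; 414/7 ≈ 59 weeks.
- With the ±7-day window, a scheduled Week 72 visit falls at Week 71 at the earliest. Since 59 < 71, no Part 2 control could have reached it by the SAP date.
- Time past Week 48 for a Part 2 control by then: at most 59 − 48 = 11 weeks.
- SAP 2.1.1.3 maps an off-schedule end-of-study visit to the next scheduled visit. A Part 2 control leaving between Weeks 48 and 59 could therefore appear under Week 72, with little time on any drug.

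**3. Part 1 controls.** Protocol 9.1 and SAP 3 give about 10 subjects already randomised to high dose. The documents do not show the dose split, so assume it is equal.
- GT005 in Part 1: 10 + 10 = 20.
- Controls at 2:1: 20/2 = 10.
- Assumed uptake of 10–40%: 0.10 × 10 = 1 to 0.40 × 10 = 4 subjects.

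**4. What that could do.** Uptake, drug effect and event probability are all assumptions here.
- BCVA: shift in control mean = share of controls on drug × drug effect. With 20% and 5 letters: 0.20 × 5 = 1 letter. The shift depends on the share, so a small control group does not reduce it, but it does make the estimate less precise.
- TEAEs: the tables are cumulative over all controls. The planned number is 202/3 ≈ 67, so 1–4 subjects are 1/67 = 1.5% to 4/67 = 6.0%. If each had a study-eye event that he or she would not otherwise have had, the control rate would rise by 1.5–6.0 percentage points. Part 2 controls past Week 48 could add to this. Actual enrolment is not given; fewer controls would mean a larger share per subject.

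The point disputes no figure in the plan; 202 is used only as the planned total.

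**The case against.** **All-data analysis is legitimate.** Using all observed data and counting all events to end of study is a recognised treatment-policy approach, and LLD, MNRead, FRI and VFQ-25 are expressly summarised on observed data. This stands, and it is why the planned analyses should be kept. It does not close the gap, because the SAP names no strategy for these endpoints and uses the opposite one for GA area at the same visits.

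**The information is recoverable.** Adverse events after alternative therapy are flagged in listings, and SAP 2.4.2 lists concomitant medication by arm with indication, route, laterality and dates. That is true, but no summary table uses it.

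**The study is exploratory and terminated.** Protocol 9.4.2 plans no inferential testing, and SAP 2.6.2 provides models and tables only as data allow. This limits the consequences and the size.

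**Person-level outcomes.** FRI and VFQ-25 have no study-eye score, the study eye is normally the worse-seeing one, and Protocol 5.6.1 allows fellow-eye GA treatment without restriction by arm. Censoring them on study-eye therapy would not restore an untreated comparison. This stands.

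**Stronger readings.** A reader might take the planned 67 controls and 10–40% uptake and infer 7–27 affected subjects. The timing above does not support that for Weeks 72–96. A reader might also infer a 20-point rise in the control event rate (0.40 × 0.50), but that multiplies the upper ends of two assumed ranges, and the event tables are cumulative rather than specific to late visits. Nor does the SAP say how often the approved drugs are given; 2.1.1.6 states only the intravitreal route.

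**Conclusion.** The gap is real and follows directly from Table 3 and the SAP's single rule. Controls may have data on an approved drug after Week 48, and the affected study-eye results do not separate them. Whether any did is not known from the documents.

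The group is probably small: about 1–4 of roughly 10 Part 1 controls, given an equal dose split, about 10 high-dose subjects and 10–40% uptake. Part 1 may have enrolled further subjects before it closed, and follow-up may have continued after the SAP date, so this is an order of magnitude.

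A reader might infer that the primary result is compromised. It is not affected by this allowance, because Table 3 bars approved GA medication in both arms to Week 48 and GA area has its own censoring rule. The matter is worth correcting before the final tables, mainly for BCVA, letter loss and study-eye adverse events.

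**What to change.** Keep every planned all-data analysis in SAP 2.6.2, 2.7.1 and 2.7.3. Beside them, add versions truncated in all arms at first alternative GA therapy in the study eye, for:
- the BCVA MMRM;
- the study-eye LLD, MNRead and retinal morphology summaries;
- the ≥15/≥30-letter loss counts for the study eye;
- the study-eye TEAE tables.

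Tabulate by arm the number of subjects starting such therapy and the start week. State which question each version answers. Do not censor FRI or VFQ-25 on study-eye therapy; report them next to the uptake table.

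SAP 2.1.1.6, which has no arm or time limit, and Protocol Table 3, which differs by arm, must be reconciled by the clinical team.

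The cost is SAP wording and a few repeat tables from data already collected. The truncated versions will have fewer late control observations. If uptake proves to be nil, the uptake table alone settles the matter.
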